6.5.5 Safety assessments

6.5.5.1 Adverse events

6.5.5.1.1 Definitions

Adverse event (AE)

An AE is any untoward medical occurrence in a patient or study patient administered a pharmaceutical product; the event does not necessarily have a causal relationship with the treatment or usage.

AEs include the following:

- Abnormal test findings, as specified below.
- Clinically significant signs and symptoms.
- Changes in physical examination findings.
- Progression/worsening of underlying disease.

In addition, signs and symptoms resulting from the following should also be handled according to the same principles as AEs:

- Overdose.
- Withdrawal of treatment.
- Interactions.
- Abuse.
- Misuse.

For pregnancies and breastfeeding, see 6.5.5.1.6

Abnormal test findings

An abnormal test finding, e.g. abnormal laboratory analysis results, vital signs, or ECG, should be recorded as an AE in any of the following situations:

- The investigator considers the abnormal test finding to be clinically significant.
- The abnormal test finding is associated with accompanying symptoms. Note, that the symptom, not the test result, should be recorded as an AE.
- The abnormal test finding leads to a medical/surgical intervention including withdrawal of IMP(s) or discontinuation from the study. Repeat/confirmatory testing is not considered a medical intervention.

Preexisting conditions

A preexisting condition (i.e., a disorder present before the AE reporting period started and noted on the pretreatment medical history/physical examination form) should not be reported as an AE unless the condition worsens, or episodes increase in frequency during the AE reporting period.

Procedures

Diagnostic and therapeutic non-invasive and invasive procedures, such as surgery, should not be reported as AEs. However, the medical condition for which the procedure was performed should be reported if it meets the definition of an AE. For example, an acute appendicitis that begins during the AE reporting period should be reported as the AE and the resulting appendectomy entered in the comments section of the eCRF.

Lack of efficacy

“Lack of efficacy” or “expected pharmacological effect has not been reached” will not be reported as an AE or SAE. However, failure of pharmacologic action or therapeutic benefit shall be recorded as an AE when they associated with a SAE or Serious outcome.

Serious adverse event (SAE)

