	
the above mentioned criteria for “Complete Response”
 
 
- In the case of “reactivated patients” who enter the study with 3 abnormal HLH features, Partial Response is adjudicated if at least 2 parameters normalize
 
- In case of reactivated patients who enter the study with 2 abnormal HLH clinical and laboratory parameters only, Partial Response is adjudicated if one of the 2 parameters normalizes
 
- There is no progression of other aspects of HLH disease pathology
 
	
at least 3 of the HLH clinical and laboratory abnormalities (including CNS abnormalities) meet the above-mentioned criteria for “Complete Response” Partial Response is adjudicated.
 
For all patients: no progression of other aspects of HLH disease pathology is assessed by absence of AEs indicating organ failure including no worsening of sCD25 levels.

HLH improvement	
HLH Improvement is adjudicated if:
 
 
- Improvement (>50% change from baseline or normalization) of at least 3 HLH clinical and laboratory abnormalities (including CNS abnormalities).
 
- In the case of “reactivated patients” who enter the study with only 2 abnormal HLH features, a change from baseline greater than 50% for both will define HLH as improved.
 
	
Definition of 50% improvement from baseline:
 
 
- Spleen size decreased by 50%, as recorded in cm from costal margin at physical examination.
 
- Absolute Neutrophil Count increased by 50%, if G-CSF has not been administered in the previous 4 days and Platelet count increased by 50%, if no platelet transfusion has been administered in the previous 4 days
 
- Ferritin decreased by 50%
 
- Fibrinogen increased by 50% or D-Dimer decreased by 50%
 
 
Normalization of CNS abnormalities = normal neurological assessment by investigator without findings in brain imaging (Brain MRI/Brain CT/cranial ultrasound), CSF analysis or AEs indicative of “CNS involvement” or “CSF abnormalities”

No Response	
If a subject does not meet the criteria for at least HLH improvement, response is categorized as “No Response”
	

Abbreviations: CNS, central nervous system; CSF, cerebrospinal fluid; G-CSF, granulocyte-colony-stimulating factor; HLH, hemophagocytic lymphohistiocytosis
		

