 AE indicating organ failures will be pre-specified according to [Appendix 1](#).

 AE indicative of CNS involvement/CSF abnormalities will be pre-specified according to [Appendix 2](#).

The treatment policy strategy will be applied. The achievement of response based on the above definition at EOT or week 8 will be estimated as described below regardless of any potential intercurrent events.

Subjects who failed to meet the definition for above categories (Complete Response, Partial Response or HLH Improvement) will be considered as No Response. The number and percentage of patients achieving Overall Response at EOT or week 8 (whichever occurs earlier), i.e., Complete Response or Partial Response or HLH improvement, as well as No Response will be provided. In addition, 95% confidence interval will be estimated using Clopper-Pearson exact method for the percentages of subjects achieving each Overall Response category. Subjects’ response status and assessments corresponding to each response criterion will be listed.

For subjects that did not withdraw treatment before week 8, observed data from the visit closest to 56 days (8 weeks) after first infusion will be used in the analysis. If there are more than one visits that are the same distance from 56 days after first infusion, data from the earlier/earliest visit will be used.

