**Appendix 1.**  
**Listing of MedDRA Terms for AE Indicating Organ Failures**

Preferred Term Code	Preferred Term
10007554	Cardiac failure
10007556	Cardiac failure acute
10024119	Left ventricular failure
10063081	Acute left ventricular failure
10039163	Right ventricular failure
10063082	Acute right ventricular failure
10051093	Cardiopulmonary failure
10038695	Respiratory failure
10001053	Acute respiratory failure
10019663	Hepatic failure
10000804	Acute hepatic failure
10077305	Acute on chronic liver failure
10019845	Hepatorenal failure
10038435	Renal failure
10077361	Multiple organ dysfunction syndrome
10053159	Organ failure
10010264	Condition aggravated

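### The Partial Response check for HLH progression can miss a progression or acute renal adverse event that is coded outside SAP Appendix 1

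*SAP*

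**What the plan says.** - **The condition.** Protocol Table 5 and SAP 6.8.2 both require for Partial Response that "There is no progression of other aspects of HLH disease pathology".
- **How it is programmed.** The SAP clarification states that, for all patients, "no progression of other aspects of HLH disease pathology is assessed by absence of AEs indicating organ failure", and the sentence goes on: "including no worsening of sCD25 levels". So there are two inputs, an adverse event list and a laboratory marker.
- **The list.** A footnote says "AE indicating organ failures will be pre-specified according to" Appendix 1, which holds 17 preferred terms. The last is "Condition aggravated". The renal entries are "Renal failure" and Hepatorenal failure.
- **Complete Response.** The same list is used: no organ-failure event is allowed. Complete Response also requires every HLH parameter that was abnormal at baseline to normalise, the others to stay normal, and no sustained rise in sCD25.
- **HLH Improvement.** This category has no condition on progression or organ failure, and it counts as Overall Response.
- **Adverse event reporting.** Protocol 6.5.5.1.1 includes "Progression/worsening of underlying disease" among adverse events. Protocol 8.3.6.1 and SAP 6.10.1 say that MedDRA is used, but give no convention for coding a worsening of HLH.
- **Supplementary definition.** SAP 6.12 repeats the same organ-failure clarification for the modified Partial Response.

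**The concern.** The condition exists to keep a patient whose disease is progressing out of the Partial Response category. The adverse event that records such progression directly is reportable, but the list recognises it only if it is coded to one generic term. Two patients with the same course, both with stable sCD25, could be classified differently because of the preferred term chosen. The renal gap works the same way: an acute renal failure coded to a term other than the two renal entries is not seen, while an acute cardiac, respiratory or hepatic failure is.

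At stake is how far the programmed response categories depend on coding. Each category is reported with an exact confidence interval, and the same definition feeds time to first response and cumulative duration of response.

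**Working it through.** No figure in the plan depends on this point, so the check is a count of the list, a trace of the rules and the size of a one-patient change.

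**1. The Appendix 1 list**

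| Group | Terms | Of these, acute |
|---|---|---|
| Cardiac, including left and right ventricular | 6 | 3 |
| Cardiopulmonary | 1 | 0 |
| Respiratory | 2 | 1 |
| Hepatic | 3 | 2 |
| Hepatorenal | 1 | 0 |
| Renal | 1 | 0 |
| Organ not specified | 2 | 0 |
| Generic worsening | 1 | 0 |
| **Total** | **17** | **6** |

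A keyword search of the 17 terms for progression, worsening, disease, kidney and the HLH word stems finds none. The stem for aggravation finds one, "Condition aggravated". Terms such as "Acute respiratory failure" show that the list keeps acute and general forms apart for other organs.

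**2. Tracing the main definition (SAP 6.8.2)**

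For cases A to C, suppose that an HLH-worsening event is reported and sCD25 has not worsened. For case D, suppose an acute renal event in a patient who meets every measured Complete Response criterion. A normalised feature is taken to satisfy HLH Improvement.

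| Case | Event coded to a listed term | Event coded outside the list |
|---|---|---|
| A. At least 3 abnormalities normalised | HLH Improvement | Partial Response |
| B. Reactivated, 3 abnormal at entry, 2 normalised, third not improved by more than 50% | No Response | Partial Response |
| C. Reactivated, 2 abnormal at entry, 1 normalised, other not improved by more than 50% | No Response | Partial Response |
| D. At least 3 abnormal at entry, all normalised | HLH Improvement | Complete Response |

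In A and D the patient is an Overall Responder either way. In D, Partial Response fails on the same list, so the patient falls to HLH Improvement. Overall Response changes only in B and C.

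**3. Size of a one-patient change**

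Shift in a category = 1/n, with n from 10 to 18 (protocol 6.1.1):

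- n = 10: 1/10 = 10.0 points
- n = 18: 1/18 = 5.6 points

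**4. Illustration for Overall Response, cases B and C only**

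Assume a rate near 60%. As a check of the Clopper-Pearson calculation, the 27/45 cited in protocol 4.1.1.3.2 gives 60.0% (44.3% to 74.3%), as stated there.

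| n | Event missed | Event counted |
|---|---|---|
| 10 | 6/10 = 60.0% (26.2% to 87.8%) | 5/10 = 50.0% (18.7% to 81.3%) |
| 18 | 11/18 = 61.1% (35.7% to 82.7%) | 10/18 = 55.6% (30.8% to 78.5%) |

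**The case against.** The case for leaving the plan alone has real content.

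- **The list is not the only safeguard.** A reader might infer that progression is judged from adverse event terms alone. The documents do not support that: sCD25 is measured at the treatment visits, needs no coding, and its worsening also blocks Partial Response. This stands, though one marker cannot represent all other aspects of the disease.
- **A worsening term is present.** A reader might infer that no progression event can be caught. An event coded to "Condition aggravated" is caught. But nothing directs HLH worsening to that term, and protocol 6.5.5.1.3 prefers a diagnosis to individual signs, which leans towards a disease-named entry. The term is also not tied to HLH.
- **Complete Response is well protected against HLH worsening.** Its measured criteria fail a patient whose scored features worsen, however the event is coded. This stands; only the renal gap matters there.
- **The modified definition looks at worsening.** SAP 6.12 withholds Partial Response and HLH Improvement when two or more parameters no longer meet normality. That helps for scored parameters. It repeats the organ-failure clarification, so the list gap remains.
- **Individual cases will be visible.** All adverse events and criterion-level assessments are listed, and investigator-assessed response is tabulated by visit. With 10 to 18 patients a discordant case could be found, but the tabulated category would still follow the algorithm.
- **Adverse event reporting is uneven.** The protocol generally excludes lack of efficacy from reporting, so extra terms will not capture every worsening. This stands as a limit on the fix.

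**Conclusion.** The gap is real and minor. As written, an HLH-progression event or an acute renal failure coded outside the 17 terms does not block Partial Response when sCD25 has not worsened, and an acute renal event outside the list does not block Complete Response.

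One such patient moves a category by 5.6 points (n = 18) to 10 points (n = 10). It would be tempting to read this as an inflation of the Overall Response rate by that amount. The documents do not support that reading: the usual result is a shift between Partial Response and HLH Improvement. When Partial Response is lost under the main definition, Overall Response changes only for reactivated patients who enter with 2 or 3 abnormal features and whose remaining feature has not improved by more than 50%.

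The conclusion rests on two assumptions that the documents cannot settle: that some HLH-worsening events will be coded to a term other than those listed, and that the MedDRA version in use has an acute renal failure term separate from the listed ones. How often either would occur cannot be determined. The study tests no hypothesis, so no error rate or power is affected.

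**What to change.** Before database lock, since the algorithm runs only afterwards:

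1. Add to Appendix 1 the preferred terms to which HLH worsening or progression is coded, and the acute renal failure term of the MedDRA version in use.
2. Apply the extended list to both the main definition (SAP 6.8.2) and the modified definition (SAP 6.12).
3. State the time window in which a listed event counts at the assessed visit. Neither response table gives one.

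The cost is a few appendix lines, a sentence on timing and a small change to the program, with no new data collection. Response categories may come out slightly less favourable.

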6.3.1 Inclusion criteria

A patient must fulfill the following criteria in order to be included in the study:

1. Male and female HLH patients of any age.
2. Patients diagnosed with confirmed or suspected pHLH, based on; a molecular diagnosis or familial history consistent with pHLH or fulfilment of HLH-2004 diagnostic criteria, i.e., five out of eight of the criteria below:

- Fever
 - Splenomegaly
 - Cytopenias affecting 2 of 3 lineages in the peripheral blood (hemoglobin <90 g/L; platelets <100 x 10⁹/L; neutrophils <1 x 10⁹/L)
 - Hypertriglyceridemia (fasting triglycerides ≥3 mmol/L or ≥265 mg/dL) and/or hypofibrinogenemia (≤1.5 g/L)
 - Hemophagocytosis in bone marrow, spleen, or lymph nodes, with no evidence of malignancy.
 - Low or absent NK-cell activity ⁱ
 - Ferritin ≥500 µg/L
 - Soluble CD25 (sCD25; i.e., soluble IL-2 receptor) ≥2400 U/mL ⁱⁱ
3. Presence of active HLH disease as assessed by the investigator.
 4. Patients must fulfil one of the following criteria as assessed by the investigator:
 - Having not responded to previous conventional treatment of HLH
 - Having not achieved a satisfactory response to previous conventional treatment of HLH or worsened
 - Having reactivated ⁱⁱⁱ
 - Showing intolerance to previous conventional treatment of HLH
- At the time of enrollment, eligible patients might still be receiving treatment (induction or maintenance) or might have already discontinued it.
5. Expectation of survival beyond 1 week as judged by the investigator.
 6. Patient has expectation of proceeding to HSCT
 7. Informed consent signed by the patient (as required by local law), or by the patient's legally authorized representative(s) with the assent of patients who are legally capable of providing it, as applicable.
 8. Willing to use highly effective methods of contraception from study drug initiation to 6 months after the last dose of study drug, if female and of childbearing potential.

In case of use of oral contraception women should have been stable on the same brand (or generic equivalent) for a minimum of 3 months before taking study treatment. Women are considered post-menopausal and not of childbearing potential if they have had 12 months of natural (spontaneous) amenorrhea with an appropriate clinical profile (e.g., age appropriate, history of vasomotor symptoms) or have had surgical bilateral oophorectomy (with or without hysterectomy) or tubal ligation at least six weeks ago.

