i NK-cell degranulation testing is considered to be acceptable

ii Or equivalent as measured by the site's laboratory

iii Reactivation is defined as:

- Deterioration of two or more HLH clinical and laboratory criteria (following an initial response) with the following specifications:

1. numerical laboratory values must become abnormal and worsen by more than 30% compared to the previous evaluation, on two sequential assessments performed with an interval of minimum 1 day and maximum 1 week*

2. deterioration of clinical criteria must be confirmed by consistent observations of worsening over three consecutive days

- The development of new or recurrent CNS symptoms counts as a single criterion for reactivation.

** The following laboratory parameters are specifically considered for determination of reactivation: platelets, neutrophils, fibrinogen, ferritin, sCD25 (i.e., soluble IL-2 receptor).*

The assessment of NK function, red blood cells/hemoglobin and triglyceride levels cannot be considered for the determination of reactivation.

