## **6.8.2. Secondary Analysis Supporting Secondary Objectives**

### Overall Response

Achievement of response will be assessed after the database lock via a programmed algorithm. The derivation of the Overall Response is detailed below.

Overall Response		
Response	Definition	Additional Clarifications
Complete Response	Complete Response is adjudicated if: 
 
- No fever = body temperature <37.5°C
 
- Normal spleen size
 
- No cytopenia = Absolute Neutrophil Counts <math>\geq 1.0 \times 10^9/L</math> and platelet count <math>\geq 100 \times 10^9/L</math> [absence of G-CSF and transfusion support must be documented for at least 4 days to report no cytopenia]
 
- No hyperferritinemia = serum ferritin level is <2000 <math>\mu g/L</math>
 
- No evidence of coagulopathy, i.e., normal D-Dimer and/or normal (>150 mg/dL) fibrinogen levels
 
- No neurological and CSF abnormalities attributed to HLH
 
- No sustained worsening of sCD25 (as indicated by at least two consecutive measurements that are > 2-fold higher than baseline)
 
	
 
- All HLH parameters that were abnormal at baseline must be normalized
 
- No AEs relating to organ failure
 
- All other parameters that were normal at baseline must still meet the definition of normalized
 
- Normal spleen size confirmed by abdominal ultrasound (US) whenever possible based on the splenomegaly not present; if US not performed physical examination will be used
 
- Normal D-Dimer levels are <math>\leq 500 \mu g/L</math>
 
- No neurological abnormalities attributed to HLH = “normal” neurological assessment by investigator in the neurological examination page (without findings in brain imaging (Brain MRI/Brain CT/cranial ultrasound) or AEs indicative of “CNS involvement”
 
- No CSF abnormalities = no AE indicative of “CSF abnormalities”
 

Partial Response	Partial Response is adjudicated if: 
 
- At least 3 of the HLH clinical and laboratory abnormalities (including CNS abnormalities) meet
 
	If a patient is not considered as “reactivated” or a patient is considered “reactivated” with 4 or more abnormal HLH features upon entry to the study and

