HLH improvement	
HLH Improvement is adjudicated if:
 
 
- At least 3 of the HLH parameters that were abnormal at baseline must be normalized or improved (i.e., <math>\geq</math> 50% change from baseline). The remaining may be the same or worse as baseline (unless 2 or more parameters no longer meet the definition of normality).
 
- In the case where a patient has only 2 abnormal HLH features at baseline, a change from baseline greater than 50% for both will define HLH as improved. The remaining may be the same or worse as baseline (unless 2 or more parameters no longer meet the definition of normality).
 
	
Definition of 50% improvement from baseline:
 
 
- Spleen size decreased by 50%, as recorded in cm from costal margin at physical examination.
 
- Absolute Neutrophil Count increased by 50%, if G-CSF has not been administered in the previous 4 days and - Platelet count increased by 50%, if no platelet transfusion has been administered in the previous 4 days
 
- Ferritin decreased by 50%
 
- Fibrinogen increased by 50% or D-Dimer decreased by 50%
 
 
Normalization of CNS abnormalities = normal neurological assessment by investigator without findings in brain imaging (Brain MRI/Brain CT/cranial ultrasound), CSF analysis or AEs indicative of “CNS involvement” or “CSF abnormalities”

No Response	
If a subject does not meet the criteria for at least HLH improvement, response is categorized as “No Response”
	

Abbreviations: CNS, central nervous system; CSF, cerebrospinal fluid; G-CSF, granulocyte-colony-stimulating factor; HLH, hemophagocytic lymphohistiocytosis
		

 AE indicating organ failures will be pre-specified according to [Appendix 1](#).

 AE indicative of CNS involvement/CSF abnormalities will be pre-specified according to [Appendix 2](#).

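### Two Overall Response rules in SAP 6.8.2 and 6.12 can misclassify a patient if coded literally: the joint neutrophil-and-platelet 50% test, and the sCD25 condition for Partial Response, which has no threshold

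*SAP*

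**What the plan says.** **Counts.** In SAP 6.8.2 (Overall Response), HLH Improvement needs a change of more than 50%, or normalisation, "of at least 3 HLH clinical and laboratory abnormalities (including CNS abnormalities"). The clarification beside it gives one bullet for blood counts: "Absolute Neutrophil Count increased by 50%, if G-CSF has not been administered in the previous 4 days and Platelet count increased by 50" per cent, with a matching four-day condition on platelet transfusion. SAP 6.12 (modified definition) words its count rule as "At least 3 of the HLH parameters that were abnormal at baseline must be normalized or improved" and repeats the joint bullet: "in the previous 4 days and - Platelet count increased by 50" per cent. Protocol Table 5 has only the general 50%-or-normalisation rule, so the joint test comes from the SAP.

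**Complete Response.** Cytopenia is a single item, starting "No cytopenia = Absolute Neutrophil Counts", with neutrophils at or above 1.0 and platelets at or above 100 (x10^9/L). The clarification for this row also deals with parameters that were normal at baseline: they must stay normal. The HLH Improvement row of 6.8.2 has no corresponding sentence.

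**sCD25.** Complete Response fails on sCD25 only if at least two consecutive measurements exceed twice baseline. In both 6.8.2 and 6.12, Partial Response is assessed by the absence of organ-failure adverse events and of any worsening in sCD25. No size, duration or number of measurements is given.

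**The concern.** Response is assigned by program after database lock, so the written rule has to fix the coding. On both items it allows two codings that can classify the same patient differently.

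Joining the two lineages does no harm in Complete Response, where a lineage that was normal already meets an absolute cut-off. It does matter for a percentage change, because a normal count has no reason to rise by half. On sCD25, the lower category carries the stricter condition if the text is read as it stands.

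Overall Response is the first-listed efficacy endpoint. The same definition drives time to first response and cumulative duration of response. The joint test could also delay the recorded date of first response for a patient whose platelets pass through a 50% rise on the way to normal.

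**Working it through.** The patients below are invented to exercise the rules. They are not trial data. Counts are x10^9/L and ferritin is in µg/L.

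**1. Can a patient enter with only one scored lineage low?** Yes. The HLH-2004 entry item is "Cytopenias affecting 2 of 3 lineages in the peripheral blood" (Protocol 6.3.1), and the third lineage, haemoglobin, is not a response item. The two-lineage combinations are Hb+neutrophils, Hb+platelets and neutrophils+platelets, so 2 of 3 leave either neutrophils or platelets normal. A patient can also enter on molecular diagnosis or family history, with no cytopenia requirement.

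**2. Joint count test.** Take a patient who is not reactivated, with three abnormal features at baseline:

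| Item | Baseline to assessment | Change | Normalised? |
|---|---|---|---|
| Fever | present to absent | – | yes |
| Ferritin | 10000 to 4000 | (10000 - 4000)/10000 = -60% | no (not below 2000) |
| Platelets | 20 to 60 | (60 - 20)/20 = +200% | no (below 100) |
| Neutrophils | 3.0 to 3.0 | 0% | normal throughout |

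Only one item normalises, so Partial Response is out.
- Literal joint test: neutrophils would have to reach 3.0 x 1.5 = 4.5. The count item fails, two items have improved, and the result is No Response.
- Test limited to the low lineage: three items have improved, and the result is HLH Improvement.

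The two codings differ only while the low lineage is up by at least 50% but not yet normal:

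| Neutrophils | Platelets | Joint test | Low lineage only |
|---|---|---|---|
| 3.0 to 3.0 | 20 to 80 | fails | passes |
| 0.4 to 0.8 | 150 to 150 | fails | passes |
| 3.0 to 3.0 | 20 to 110 | passes (normalised) | passes |
| 0.4 to 0.7 | 20 to 40 | passes (both low, both up) | passes |

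**3. sCD25 in Partial Response.** With baseline 5000, the last two values are judged as follows:

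| Last two values | Any rise | One value >2-fold | Two consecutive >2-fold |
|---|---|---|---|
| 5000, 7500 | worse | not worse | not worse |
| 6000, 11000 | worse | worse | not worse |
| 10500, 11000 | worse | worse | worse |

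What follows from losing Partial Response on sCD25 alone:
- Three or more items normalised: HLH Improvement has no sCD25 condition of its own and is already met in 6.8.2, so the patient stays a responder with a different label.
- Reactivated, three features at entry (fever, ferritin, spleen), two normalised, spleen unchanged, sCD25 5000 then 7500: Partial Response under the two-fold rule. With no threshold, Partial Response is lost and HLH Improvement needs three items, so the result is No Response.
- Reactivated, two features, one normalised, the other unchanged: the same loss, because HLH Improvement needs both.

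In 6.12 the Definition column extends the two- and three-feature rules beyond reactivated patients. Its clarification still describes three normalised items for those not reactivated, so the reach there is itself unclear.

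**4. Size of one reclassification.** The SAP specifies Clopper-Pearson intervals. As a check of method, 27/45 gives 60.0% (44.3 to 74.3), matching Protocol 4.1.1.3.2. Taking a rate near 60% for illustration only:

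| n | Responders | Rate | Exact 95% CI |
|---|---|---|---|
| 18 | 11 | 61.1% | 35.7 to 82.7 |
| 18 | 10 | 55.6% | 30.8 to 78.5 |
| 10 | 6 | 60.0% | 26.2 to 87.8 |
| 10 | 5 | 50.0% | 18.7 to 81.3 |

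One patient is 1/18 = 5.6 points or 1/10 = 10 points.

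**The case against.** **The SAP does not say a normal lineage must rise.** This is fair. The clarification is silent on the case, and the Definition columns count abnormalities, which a normal neutrophil count is not. A reader might infer that the plan positively requires a rise in both lineages when only one was low. The documents support less: a bullet that produces this result if coded as written, beside a column that points the other way.

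**The conjunction may be deliberate.** The coagulation bullet in the same list uses an either-or, and Complete Response also joins the two lineages. If so, the SAP should state that a normal lineage is tested too, because its own Definition column suggests otherwise.

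**The sCD25 threshold is one row above, and Partial Response refers back to the Complete Response criteria.** Carrying it down is the natural reading. However, the row drops the idea of a sustained rise and does not cite the rule, and Appendix 1 lists no sCD25 term. A reader might also point to the reactivation definition in Protocol 6.3.1, where values must "worsen by more than 30% compared to the previous evaluation, on two sequential assessments", as a competing rule. The SAP does not invoke it for response, so it is not evidence of a conflict.

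**Neutrophils and platelets should simply count as one item.** The documents do not settle this. Complete Response treats them as one, while the protocol's reactivation footnote lists them apart: the "laboratory parameters are specifically considered for determination of reactivation: platelets, neutrophils, fibrinogen, ferritin, sCD25". The dash in the 6.12 bullet proves nothing, since it may come from text extraction. Imposing one item for entry counting would do harm. A patient reactivated on platelets and neutrophils alone would have one feature, while the reactivated rules start at two and the general rules need three. Neither Partial Response nor HLH Improvement would then be reachable.

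**The programming specifications may resolve it, and the listings show each criterion.** Both are true as far as they go. The specifications named in SAP 11.2 were not available for this review. The listings would expose a disputed case but not say which result was planned.

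**Conclusion.** The point stands, at minor to moderate severity. Two stated rules can misclassify a patient if programmed literally. The joint count test can turn HLH Improvement into No Response, but only when a single low lineage has risen by at least 50% without normalising and that item decides the count. The sCD25 wording makes Partial Response stricter than Complete Response. Usually it only changes the label, and it affects responder status only for some patients under the two- or three-feature rules.

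Each reclassified patient is worth 5.6 to 10 points of a descriptive rate whose exact intervals are about 47 to 63 points wide. The number of such patients cannot be derived from the documents. A reader might infer that the reported response rate will be materially biased, but nothing in the documents supports a size or frequency beyond the single-patient figure. No hypothesis test or primary endpoint depends on it. The conclusion assumes that the programming specifications do not already fix both readings.

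**What to change.** Amend SAP 6.8.2 and 6.12 before database lock and record it in the Modification History:

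1. Apply the +50% or normalisation test, with its four-day support condition, only to the lineage or lineages abnormal at baseline. Require both only when both were abnormal.
2. For Partial Response, define worsening of sCD25 by citing the Complete Response rule (two consecutive values above twice baseline).
3. If the SAP also states whether neutrophils and platelets are one feature or two, keep a response route for patients reactivated on those two alone.

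The cost of items 1 and 2 is a few lines of text and code, with no new data. Item 3 needs more thought because it touches the feature counts at entry. The real downside is direction: against the literal text, edits 1 and 2 can only add responders or raise a response category. In an open-label study whose SAP is already at version 4.0, the amendment therefore has to be dated before lock, with the reason given. If the sponsor intends the stricter readings, stating them explicitly would also close the gap.
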